3.4 Eligibility Criteria

3.4.1 Inclusion Criteria

1. Singleton gestation. Twin gestation reduced to singleton either spontaneously or therapeutically, is not eligible unless the reduction occurred before 13 weeks 6 days project gestational age (see below). Higher order multifetal gestations reduced to singletons are not eligible.

2. Gestational age at randomization between 16 weeks 0 days and 23 weeks 6 days based on clinical information and evaluation of the earliest ultrasound as described in Gestational Age Determination in Section 3.4.2 below.
3. Cervical length on transvaginal examination of less than or equal to 20 mm by a study certified sonographer. There is no lower cervical length threshold.

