3.6 *Randomization Method and Masking*

Consenting women will be assigned to one of the two arms by using an internet based randomization system maintained centrally by the Biostatistical Coordinating Center (BCC).

The simple urn method will be used to generate the randomization sequences because it provides a high probability of balance in treatment assignments, it is unpredictable, and it allows an explicit randomization analysis to be conducted with relative ease. Randomization will be stratified by clinical site to assure balance between the two arms with respect to anticipated differences in the clinic populations and possible differences in patient management.

4 Study Procedures

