4.6.2 Maternal Secondary Outcomes

1. Interval from randomization to delivery or fetal demise
2. Gestational age at delivery
3. Preterm delivery or fetal demise prior to 28 weeks, 32 weeks or 35 weeks
4. Preterm premature rupture of membranes (pPROM)
5. Spontaneous preterm delivery (following preterm labor or pPROM)
6. Indicated preterm delivery

7. Cesarean delivery
8. Chorioamnionitis
9. Maternal antepartum hospitalization days
10. Maternal antibiotic or antifungal use for vaginal infection
11. Vaginal infection as assessed by local clinical diagnosis
12. Treatment for preterm labor, including cervical cerclage
13. Side effects including symptomatic vaginal discharge or discomfort
14. Discontinuation of pessary treatment and reason

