5.2 Sample Size and Power

A one-third reduction in preterm birth < 37 weeks was selected as being clinically meaningful. If it is conservatively assumed that the rate of preterm birth < 37 weeks in the progesterone arm is between 28% and 35%, then a sample of 850 women is sufficient to detect a 33% reduction in preterm birth at 90% power. In addition this sample size yields more than 80% power to detect a 30% reduction, assuming a type 1 error of 5% 2-sided.

Table 2. Sample Size for Various Outcome Rates and Effect Sizes

PTB rate in Usual care arm (%)	Total sample size for 30% reduction	Total sample size for 33.3% reduction
Power=80% ($\alpha=0.05$; $\beta=0.2$)		
28	810	640
30	740	590
32	680	540
35	600	480
Power=90% ($\alpha=0.05$; $\beta=0.1$)		
28	1080	850
30	990	790
32	900	720
35	800	640

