5.5 Analysis Plan

All statistical analyses will be based upon the total cohort of patients randomized into the trial. Although data on some patients may be missing, all relevant data available from each patient will be employed in the analyses. Patients will be included in the treatment group to which they were randomly assigned regardless of compliance.

The primary analysis will consist of a simple comparison of binomial proportions. The relative risk and confidence interval will be reported. The individual components of the composite outcome will also be examined. If the treatment groups are found to differ on a pre-treatment factor known to be a risk factor for the outcome, the statistical analysis will adjust for these differences. An evaluation of treatment by center interaction will be included. An analysis adjusting by center also will be performed to ensure that center differences do not change the conclusion.

If the two groups show a difference in the incidence of the primary outcome, interactions will be evaluated and subgroup analyses conducted to determine whether the effect prevails throughout particular subgroups of patients. Indeed, NIH guidelines require investigators to evaluate consistency between the genders and across racial subgroups (see Section 5.5.1). It should be noted, however, that subgroup analyses have been greatly abused, particularly when there is no overall treatment difference.³⁶ There is a strong temptation to search for a specific subpopulation in which the therapy is nevertheless effective. Yusuf et al. concluded "the overall 'average' result of a randomized clinical trial is usually a more reliable estimate of the treatment effect in the various subgroups examined than are the observed effects in individual subgroups."³⁷ Thus subgroup analyses will be interpreted with care.

It is generally acknowledged that subgroup analysis that is pre-specified in the protocol has more validity than ad-hoc comparisons. The following factors will be considered for subgroup analysis, if there is a significant interaction between the factor of interest and the treatment effect.

- Race/ethnicity (see below)
- Gestational age at randomization (< 20 weeks and \geq 20 weeks)
- Cervical length at randomization (< 15 and \geq 15 -20 mm)
- Treatment with vaginal progesterone (as planned per usual care locally)
- Screening to randomization interval
- Debris/funneling on randomization ultrasound
- Obesity by BMI category
- Parity

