- Bacterial vaginosis/Nugent score at enrollment—Nugent \geq 7 with pH > 4.4
- Prior cervical surgery including LOOP/ LEEP

Loss to follow-up will be defined as no information regarding pregnancy prior to 37 weeks. Those defined as lost to follow-up will not be included in the primary analysis. It is expected that the loss to follow-up rate will be very low. For trials conducted by the MFMU Network, the loss to follow-up rate has typically been under 2 percent. However, a sensitivity analysis will be performed including patients lost to follow-up with different assumptions regarding their outcome, to determine whether the results are robust.

Since many of the secondary endpoints are dichotomous variables like the primary outcome, standard statistical methods for rates and proportions will be appropriate. The Wilcoxon rank sum test will be used to compare continuous variables, and survival analysis methodology may be used to compare time-to-event variables.

In general, analyses of data will be conducted to address the primary and secondary research questions of the trial, and other interrelationships among elements of study data of interest to the investigators and of relevance to the objectives of the study.

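### The randomization-to-delivery interval is to be tested without adjusting for gestational age at randomization, a known component of it; prespecified adjustment would give a modest, nearly free gain in precision

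*Combined protocol and SAP*

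**What the plan says.** - **Outcomes.** Section 4.6.2 lists as maternal secondary outcome 1 the "Interval from randomization to delivery or fetal demise" and as outcome 2 "Gestational age at delivery".
- **Entry window.** Section 3.4.1 requires "Gestational age at randomization between 16 weeks 0 days and 23 weeks 6 days". Under section 3.4.2 the project gestational age is settled before randomization and the due date based on it is not revised.
- **Test.** Section 5.5: "The Wilcoxon rank sum test will be used to compare continuous variables, and survival analysis methodology may be used to compare time-to-event variables". The Wilcoxon test is a commitment and the survival methods are optional. Neither comes with a covariate.
- **Adjustment.** The only adjustment rule for pre-treatment factors in section 5.5 follows the description of the primary analysis. If the groups turn out to differ on a pre-treatment factor that is a known risk factor, "the statistical analysis will adjust for these differences".
- **Other uses of entry age.** In section 5.5 it otherwise appears only as a subgroup factor, "Gestational age at randomization (< 20 weeks" against later entry. It is not a stratification factor: section 3.6 says "Randomization will be stratified by clinical site" and names nothing else.

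**The concern.** The interval contains gestational age at randomization with coefficient −1 by construction. That value is known exactly for every woman before allocation and has nothing to do with treatment. Under the design rates, 72% of the usual-care arm deliver at term, within a narrow range of gestational ages. Among those women the length of the interval largely reflects when they were enrolled. An unadjusted rank test leaves this known variation in the comparison. With balanced arms, the conditional adjustment rule is never triggered.

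What is at stake is precision on one secondary outcome. The interval result could be less clear than the result for gestational age at delivery for a reason unrelated to the pessary.

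**Working it through.** **Inputs from the documents.** 425 per arm (850 with 1:1 allocation; section 5.2, Appendix A). Event rates 28% and 18.67% (Appendix A). Alpha 5% two-sided (section 5.2; Appendix A prints 2.5%, but 5% is the value that reproduces 850). Entry window as in section 3.4.1. The documents give no SD or distribution for entry age, delivery age or the interval, so those below are assumptions, shown as ranges.

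**1. The plan's own figure.** After its assumed rates, section 5.2 continues "then a sample of 850 women is sufficient to detect a 33% reduction in preterm birth at 90% power". Unpooled formula, per arm: (1.960 + 1.282)² × (0.28 × 0.72 + 0.1867 × 0.8133) / (0.28 − 0.1867)² = 10.507 × 0.3534 / 0.00871 = 426.3, or 853 in total. The pooled formula gives 860, and power at 425 per arm is 89.7%. The figure reproduces. It concerns the primary outcome only; no power is stated for the interval.

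**2. Share of the interval that is entry age.** The window is 7.86 weeks wide, so evenly spread entry has SD 7.86/√12 = 2.27 weeks. For term births with an assumed SD of 1.1 weeks, the share of interval variance due to entry age is s²/(s² + 1.21):
- s = 1.0: 1/2.21 = 45%
- s = 1.5: 2.25/3.46 = 65%
- s = 2.27: 5.15/6.36 = 81%

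**3. Normal approximation.** If entry and delivery ages are independent, the interval variance is SD_del² + SD_entry², and adjustment removes the second term. Where the adjusted comparison has 80% power, the unadjusted power is Φ[(1.960 + 0.842)/√V − 1.960], with V = 1 + SD_entry²/SD_del².

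| SD entry (wk) | SD delivery (wk) | V | 850 is worth | Unadjusted power |
|---|---|---|---|---|
| 1.0 | 4.5 | 1.05 | 810 | 78.1% |
| 1.0 | 3.5 | 1.08 | 786 | 76.8% |
| 1.5 | 4.5 | 1.11 | 765 | 75.7% |
| 1.5 | 3.5 | 1.18 | 718 | 73.1% |
| 2.27 | 4.5 | 1.25 | 678 | 70.6% |
| 2.27 | 3.5 | 1.42 | 598 | 65.2% |

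**4. Simulation, first set of assumptions** (2,000 trials per row, 425 per arm). Term births: mean 39.1 weeks, SD 1.1, limited to 37–42. Preterm births: spread between entry and 37 weeks, skewed late. Power (%), entry age unrelated to preterm risk:

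| Entry SD (wk) | Wilcoxon, interval | Wilcoxon, interval adjusted for entry age | Wilcoxon, gestational age at delivery | Rank ANCOVA, interval |
|---|---|---|---|---|
| 1.0 | 63.4 | 64.8 | 65.2 | 71.1 |
| 1.4 | 60.8 | 65.6 | 65.2 | 74.0 |
| 1.7 | 60.8 | 67.6 | 67.6 | 77.2 |
| 2.27 (even) | 56.1 | 66.4 | 67.0 | 78.4 |

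The gains from column 2 to column 3 are 1.4, 4.8, 6.8 and 10.3 points. With earlier entry carrying higher risk (log-odds −0.15 per week) they fall to 0.8, 1.9, 2.4 and 6.4. Type I error for the Wilcoxon tests on the interval and for rank ANCOVA was 4.7–5.2%, checked at SD 1.4 and even entry.

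**5. Simulation, second set** (3,000 trials per scenario). Preterm births were placed in fixed bands (20–24, 24–28, 28–32, 32–35, 35–37 weeks) with weights .03/.05/.05/.06/.09 or .01/.02/.03/.07/.15. Term births had mean 39.2, SD 1.1. Power (%):

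| Entry | Wilcoxon, interval | Stratified by week of entry | Rank ANCOVA |
|---|---|---|---|
| SD 1.0 | 61–62 | 63 | 70–71 |
| SD 1.5 | 57–60 | 65 | 73–75 |
| Even | 45–52 | 65–66 | 75–76 |

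In a 1,500-trial run of the same setting, plain Wilcoxon on gestational age at delivery, which contains no entry-age noise, reached 64–66% throughout. The shortfall of the unadjusted interval against it was about 3–4, 6–9 and 14–23 points.

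**6. Survival route.** In the first set, stratifying the log-rank test by week of entry added 3–6 points when entry age was unrelated to risk (for example 31.3% to 37.0% with even entry). It cost 2–4 points when earlier entry was riskier (39.4% to 35.3%).

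**7. Chance imbalance.** The SD of the between-arm difference in mean entry age is SD_entry × √(2/425): 0.07 weeks at SD 1.0 and 0.16 at 2.27. The mean prolongation in the second set is about 0.75 weeks.

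**The case against.** **Outcome 2 already does the job.** Gestational age at delivery goes through the same Wilcoxon test without the noise and reaches about 65% power here. Its wording does not mention demise, but a woman with a fetal demise still delivers. The two outcomes then differ only by the gap between demise and delivery in few cases, and demise also counts in the primary outcome and in outcome 3. This largely stands. It limits the importance of the point but does not make the interval analysis efficient.

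**The large losses need evenly spread entry.** Section 8.2 ties detection to a mid-trimester ultrasound, and section 3.4.4 requires an anatomy scan between 14w0d and 23w6d. Neither shows how entry ages will be distributed. The upper figures are therefore possible, not expected.

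**Section 5.5 can already adjust.** The conditional rule could cover a material imbalance, and a survival model with a covariate is not excluded. Both are true, but neither is a prespecified precision adjustment.

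**Stronger readings a reader might infer:**
- *That adjustment is worth up to 30 points.* Rank ANCOVA exceeds even the noise-free Wilcoxon on gestational age at delivery (71–78% against 65–68% in the first set). Part of its advantage therefore comes from the different statistic, not from removing the baseline term.
- *That chance imbalance in entry age could drive the result.* At 0.07–0.16 weeks against about 0.75, this is weak.
- *That a survival analysis should be stratified by week.* Step 6 shows that this can lose power.

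**Conclusion.** The point holds as a minor efficiency improvement to one secondary outcome. Removing the known baseline term recovers roughly 1–4 points of power if entry ages have an SD near 1 week, about 5–10 at SD 1.5, and about 6–20 if entry is spread evenly over the window. The gain is smaller where earlier entry carries higher risk. Rank ANCOVA gained about 7–30 points across the simulations, for the mixed reason given above. All these figures rest on assumed gestational-age distributions.

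The documents do not support reading the planned test as biased or invalid: randomization protects it, and its simulated type I error is nominal. Nor does the interval's place at the head of the lists in section 4.6.2 and Appendix A make it a key secondary outcome. The plan states no hierarchy, and the itemised questions in section 3.2 do not name it.

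**What to change.** Add one sentence to section 5.5: outcome 1 is compared by a rank-based analysis of covariance with project gestational age at randomization as covariate, whether or not the arms differ on it.

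Name that one method and not a list of alternatives, since the candidates differ in power. A Wilcoxon test stratified by week is a less dependable choice: in further runs its gain fell to between about −1 and +4 points when entry was clustered or earlier entry was riskier, apart from larger gains in some spread-entry cases. Make no recommendation to stratify a log-rank or Cox analysis by week.

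The cost is small. The covariate is already determined for every woman before randomization, so no new data are needed. The one downside is a test slightly less familiar than a plain Wilcoxon. Fixing it in advance also removes discretion over adjustment after baseline differences have been seen.

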5.5.1 Racial/Ethnic Subgroup Analysis

The racial/ethnic composition of women recruited into the MFMU Network trials varies. Assuming for this trial that the composition is 50% African-American and 15% Hispanic, similar to the SCAN trial there is >90% and approximately 50% power respectively to detect a 50% reduction in the primary outcome in the separate subgroups.

6 Data Collection

6.1 Data Collection Forms

Data will be collected on standardized forms on which nearly all responses have been pre-coded. Each form is briefly described below:

- TO01 Screening Log.
- TO01A Eligibility Checklist
- TO02 Eligibility and Randomization Form is completed for all patients eligible for the study.
- TO03A Pessary Accountability Log lists the specific pessary(ies) given to each patient.
- TO04 Baseline Form is completed for all randomized patients. This form includes detailed demographic and social data, medical and obstetrical history, and current pregnancy complications.
- TO04A Previous Pregnancy Outcome Form.
- TO05 Study Visit Form documents monthly study visits, possible side effects and compliance
- TO07 Unscheduled Visit or Hospitalization Form is completed for all patients who had an unscheduled emergency room, Labor & Delivery, clinic visit or hospitalization between the scheduled monthly visits, including the delivery admission.
- TO08 Maternal Delivery and Outcome Form documents specific pregnancy complications since randomization, in addition to labor, delivery and postpartum information.
- TO09 Neonatal Baseline Form records date and time of birth, delivery data and status at delivery, for each fetus/infant.
- TO10 Neonatal Outcome Form records outcome data for all infants admitted to the NICU or special care nursery.
- TO11 Patient Status Form documents loss to follow up/withdrawal status, last date of contact for lost to follow-up patients, side effects since the last dose.
- TO12 Adverse Event Form records serious and non-serious adverse events.
- TO13A Women's Views on the Arabin Pessary, a patient questionnaire.
- TO14 Pessary Removal Form documents the position of the pessary at the time of removal.

6.2 Web Data Entry System

For this protocol, web data entry screens corresponding to the study forms listed above will be developed and maintained by the staff of the BCC. Clinical center staff will enter data into the MySQL database located at the BCC through a web data management system (MIDAS). The data are edited on-line for missing, out of range and inconsistent values. A Users' Manual documenting this system is provided to the centers by the BCC.

6.3 Centralized Data Management System

Daily data conversions from the MySQL database create up-to-date SAS datasets. Data are reviewed weekly using edit routines similar to those implemented on-line during data entry, as well as additional checks for data consistency within or across forms. A database of resulting potential data problems is generated in MIDAS for initial review by BCC staff who then evaluate the comments keyed in association with edits on missing or unusual values. Valid edits will be flagged in MIDAS for resolution at the clinical centers.

At regular intervals, specialized data reviews comparing data availability and consistency across forms are run by the BCC staff on the entire database or on a specific subset of data. These reports are also submitted to the centers for correction or clarification.

An audit trail, consisting of all prior versions of each data form as entered in the computer for each patient, is maintained so that the succession of corrections can be monitored.

6.4 Performance Monitoring

The BCC will present regular reports to the TOPS Subcommittee, the Steering Committee, and the Data and Safety Monitoring Committee. These include:

- Monthly Recruitment Reports - reports of the number of women screened and enrolled by month and by clinical center are provided monthly to the TOPS Subcommittee and all other members of the Steering Committee. Weekly or bi-weekly reports are provided electronically if needed.
- Quarterly Steering Committee Reports - reports detailing recruitment, baseline patient characteristics, data quality, incidence of missing data and adherence to study protocol by clinical center, are provided quarterly to the TOPS Subcommittee and all other members of the Steering Committee.
- Data and Safety Monitoring Committee Reports - for every meeting of the DSMC, a report is prepared which includes patient recruitment, baseline patient characteristics, center performance information with respect to data quality, timeliness of data submission and protocol adherence (in addition to safety and efficacy data). The reports also include adverse events, loss to follow-up and all outcome variables as described previously in this protocol.

7 Study Administration

7.1 Organization and Funding

The study is funded by the *Eunice Kennedy Shriver* National Institute of Child Health and Human Development (NICHD). The study is conducted by the NICHD Maternal-Fetal Medicine Units (MFMU) Network, consisting of twelve clinical centers, the Biostatistical Coordinating Center (BCC) and the NICHD, and is administered under cooperative agreements between each of the centers and the NICHD. Each of the funded institutions is represented by a Principal Investigator. A complete description of the organization of the MFMU Network is provided in the MFMU Network Policy Manual.

7.1.1 Participating Clinical Centers

The participating Principal Investigators of the clinical centers have agreed to abide by the study protocol, to have comparable staff, facilities and equipment and to ensure the proper conduct of the study at each of their centers including: recruitment and treatment of patients as specified in the protocol, accurate data collection and the transmission of information to the Steering Committee.

7.1.2 Biostatistical Coordinating Center

The BCC is responsible for all aspects of biostatistical design, data management, interim and final statistical analyses, and preparation of publications based on the study results. The Principal Investigator of the BCC reports to the Steering Committee and the Data and Safety Monitoring Committee.

7.1.3 NICHD

In addition to its role as funding agency, the NICHD participates in the activities of the Network, including the development of protocols, administration and conduct of the studies and preparation of publications.

7.1.4 Network Advisory Board

Appointed by the NICHD, the members of the Network Advisory Board consist of a group of experts who are not affiliated with research being conducted by the Network and represent the disciplines of maternal-fetal medicine, neonatology and biostatistics/epidemiology. The role of the board includes the review and prioritization of proposed studies, in addition to the identification of scientifically and clinically important questions and ideas that might be conducted by the Network. The NICHD Project Scientist convenes and attends the meetings.

7.2 Committees

7.2.1 Steering Committee

This committee consists of fifteen members. The Principal Investigator from each of the twelve clinical centers, the BCC, and the NICHD MFMU Network Project Scientist are all voting members. The Chair of the Steering Committee may vote to break a tie. The Chair, a person independent of the participating institutions, is appointed by NICHD. The Steering Committee has the responsibility for identifying topics for Network studies, designing and conducting study protocols and monitoring study implementation, recruitment and protocol adherence. The committee receives recommendations from the Data and Safety Monitoring Committee and the Network Advisory Board.

